**7.4.1 Study Therapy**

**7.4.1.1 Therapy with BMS-986158**

**Summary 1:**

Descriptive statistics will be provided by treatment and overall for the following.

- Number (%) of treated subjects exposed for specified periods of time such as less than or equal to 1 week, more than 1 but less than 4 weeks, etc.

**Summary 2:**

Descriptive statistics will be provided by treatment and overall for the following.

- **Number of actual BMS-986158 doses**
- **BMS-986158 Duration of therapy (weeks)**
  - The  $(\text{last dosing date} - \text{the first dosing date} + \text{DI}) / 7$ , where DI is the dosing interval between the end of the scheduled dose(s) and the start of the next dose(s) in days for the study part and dosing schedule(s) administered; the denominator (7) scales the duration to units of weeks.
  - As Part 1 consists of a single dose delivered in the first 7 days (Cycle 1), without plan to be repeated, a dosing interval in this schedule is not defined, and Part 1 Cycle 1 will not be included in the summary of the exposure.
  - **Dosing Interval (DI)** number of days between planned set of doses per a schedule is:
    - Part 1 and Part 2, while “on” dose during the “on cycle”, DI=1 day
    - Part 1, Schedule A, Cycle 2 and beyond, and Part 2, Schedule A: (5 single daily doses followed by 2 days of no dosing per week), after 4th consecutive dose for 7 day cycle, DI=2 days

- Part 1, Schedule B (Three Week dosing schedule), after 13th consecutive dose for 14 day cycle, DI=7 days
- Part 1, Schedule C (Three Week dosing schedule), after 6th consecutive dose for 7 day cycle, DI=14 days
- The duration of therapy will be adjusted for subjects who are known to have died prior to receiving the next dose by using instead of DI the number of days between the death date and the last dose date. For subjects who discontinued or were lost to follow-up, DI will be
  - Parts 1, 2, using Schedule A, DI= 1 day if they received  $\leq 3$  of the 5 doses, and DI= 2 if they received 4 or 5 doses.
  - Part 1, using Schedule B, DI will still be set to 7 days if discontinued or lost to followup.
  - Part 1, using Schedule C, DI will still be set to 14 days if discontinued or lost to followup.
- Duration of therapy for subjects admitted to Study Part 1 will be left censored to exclude the single dose administered on Cycle 1 Day 1. The dose administered on Cycle 2 Day 1 will be considered to establish the date of first dose for dose intensity and relative dose intensity calculation.
- **BMS-986158 cumulative dose (mg)** is the sum of the actual doses administered to a subject
- **BMS-986158 dose intensity (mg/week)** per subject is the ratio of the cumulative dose (mg) to the duration of therapy (weeks) for the study part to which the subject is enrolled:
- **BMS-986158 relative dose intensity (%)** is the ratio of the dose intensity (mg/week) to the planned dose level per week and is scaled to units of percent for presentation.
  - Relative dose intensity will be summarized using categories:  $<50\%$ ;  $50 - < 70\%$ ;  $70 - < 90\%$ ;  $90 - < 110\%$ ;  $\geq 110\%$

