No treatment-related deaths have been reported in any treatment cohort of Study CA011-001. Nine deaths were reported in participants treated with BMS-986158 monotherapy within 30 days of last dose. Of the 9 deaths, 8 deaths were reported as secondary to disease and 1 due to cerebrovascular accident; all of which were considered not related to BMS-986158 treatment.

A total of 68 subjects were discontinued from study treatment due to disease progression.

A detailed description of BMS-986158 safety is provided in the IB.

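### SAP 7.4.1.1: the death adjustment to duration of therapy has no cap, and its precedence over the discontinuation rule is not stated

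*SAP*

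**What the plan says.** SAP 7.4.1.1, Summary 2, defines duration of therapy in weeks as (last dosing date − first dosing date + DI)/7. DI is 1 day within a dosing block. At the end of a block it is 2 days on Schedule A, 7 on Schedule B ("Part 1, Schedule B (Three Week dosing schedule), after 13th consecutive dose for 14 day cycle, DI=7 days") and 14 on Schedule C.

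Two exceptions follow.

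- **Death.** Duration is adjusted for those "known to have died prior to receiving the next dose by using instead of DI the number of days between the death date" (counted from the final dose). There is no upper limit, and the next dose is not described as the next scheduled one.
- **Discontinuation.** "For subjects who discontinued or were lost to follow-up, DI will be" a fixed number: on Schedule A, 1 day after three or fewer of the five weekly doses and "DI= 2 if they received 4 or 5 doses"; on Schedule B, 7 days; on Schedule C, 14 days.

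Dose intensity is cumulative dose divided by this duration. RDI "is the ratio of the dose intensity (mg/week) to the planned dose level per week", tabulated in five categories with cut-points at 50, 70, 90 and 110%.

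**The concern.** Anyone who dies after a last dose has, literally, died before receiving another. Without a cap or a link to the schedule, the wording can add all the time from last dose to death to the time on therapy. A subject who discontinued and then died meets both sentences, so two programmers could derive materially different values from the same data.

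A second group is exposed even if the discontinuation rule takes precedence. A subject who dies during a dose hold, without being recorded as discontinued, falls only under the death sentence. Protocol 4.5.2 permits holds of up to 30 days, and longer ones by agreement.

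Duration is the denominator of dose intensity and RDI, which help describe how well the regimen was delivered. Safety, tolerability and the recommended Phase 2 dose form the primary objective (SAP 3.1). Off-drug time before death could appear as poor dose delivery in a subject who missed no dose.

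**Working it through.** The plan states no result for this rule, so there is no figure to reproduce. The check applies the SAP's definitions to fully dosed subjects.

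**Inputs.** DI at the end of a block is 2, 7 or 14 days for Schedules A, B and C (SAP 7.4.1.1). Part 1 counts from Cycle 2 Day 1, because the SAP excludes the single Cycle 1 dose. Assumptions: a constant dose level, no missed dose, and last dose at the end of a block. The time g from last dose to death is also an assumption, varied from 1 to 180 days, because the documents do not give it.

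**Formula.** Let W be the planned weeks completed and S the days from first to last dose. Cumulative dose is W × planned weekly dose, and duration is (S + g)/7. The dose level cancels, so RDI = 7W/(S + g). With no death, DI takes the place of g.

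- A, four weeks: W = 4, S = 25 (day 1 to day 26), RDI = 28/(25 + g)
- B, two cycles: W = 6, S = 34 (day 1 to day 35), RDI = 42/(34 + g)
- C, two cycles: W = 6, S = 27 (day 1 to day 28), RDI = 42/(27 + g)

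| Schedule | Stated DI | Death at 1 day | 7 days | 14 days | 30 days |
|---|---|---|---|---|---|
| A | 28/27 = 103.7% | 107.7% | 87.5% | 71.8% | 28/55 = 50.9% |
| B | 42/41 = 102.4% | 120.0% | 102.4% | 87.5% | 42/64 = 65.6% |
| C | 42/41 = 102.4% | 150.0% | 123.5% | 102.4% | 42/57 = 73.7% |

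The fully dosed values exceed 100% because the stated DI is one day shorter than the gap from the last dose of one block to the first of the next (3, 8 and 15 days).

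**Direction.** Duration is lengthened only when g exceeds DI, that is, more than 2, 7 or 14 days on A, B and C. Earlier deaths shorten it and raise RDI.

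**Size on Schedule A, four weeks.** Duration goes from 27/7 = 3.86 weeks to 55/7 = 7.86 weeks at g = 30. RDI leaves the 90 to <110% category from g = 7 (87.5%) and falls below 50% from g = 32 (28/57 = 49.1%). After eight weeks of treatment (W = 8, S = 53) the drop at 30 days is smaller: 56/55 = 101.8% to 56/83 = 67.5%.

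**If the death rule overrides the discontinuation rule.** On Schedule A, four weeks, RDI is 28/115 = 24.3% at 90 days and 28/205 = 13.7% at 180 days, with duration 205/7 = 29.3 weeks in the latter case. Under the discontinuation rule the same subject keeps DI = 2 and 103.7%.

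**With a cap of min(DI, g).** The 30-day values return to 103.7%, 102.4% and 102.4%. Values for deaths within DI do not change.

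**The case against.** The natural reading is the benign one. In a paragraph about the interval to the next dose, a rule for death before that dose most plausibly truncates DI when death falls inside it. The next sentence also gives discontinued subjects a fixed DI, and a subject who stopped for progression has discontinued. On that reading the 90- and 180-day values never arise. Both arguments are sound and limit the point to an ambiguity, but neither supplies a cap nor says which sentence wins. Even the dose-hold case is arguable: for a subject who resumes dosing, hold time already counts through the first and last dosing dates. The remaining inconsistency is with a subject who stops drug on the same day, with identical dosing, and is recorded as discontinued.

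The reach is narrow. Number of doses and cumulative dose are unaffected. Exposure-adjusted adverse event rates have their own exposure definition (SAP 7.6.6), DLT evaluability counts doses, and no efficacy endpoint uses this duration. The planned listings of dosing and derived exposure would make an odd value traceable.

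Three stronger readings are tempting and are not supported.

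- A reader might infer that the rule systematically inflates duration in everyone who died. Deaths inside DI go the other way.
- A reader might take the Protocol 1.4.4 statement that "Nine deaths were reported in participants treated with BMS-986158 monotherapy within 30 days of last dose", set against 81 treated, as the share affected. That section gives neither the individual gaps nor whether those subjects had already discontinued.
- A reader might assume that most subjects are followed to death. SAP 6.1.2 ends survival follow-up at 2 years from first dose (unless treatment continues longer) or 6 months after last treatment, whichever is later.

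**Conclusion.** The point holds as a gap in a derivation rule. The death adjustment has no cap, the next dose is not tied to the schedule, and precedence over the discontinuation rule is missing. Taken literally, a death later than DI counts off-drug time as therapy and can roughly halve RDI in a fully dosed subject: 103.7% to 50.9% at 30 days on Schedule A after four weeks. That figure assumes full dosing at a constant level and that the death sentence governs, which is clearest for a subject who dies on a dose hold. The much lower 90- and 180-day figures additionally require the death rule to override the discontinuation rule, which the SAP does not say. The number of subjects affected cannot be determined from the documents.

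Severity is minor: the effect is confined to the descriptive summaries of duration, dose intensity and RDI categories.

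**What to change.** In SAP 7.4.1.1, replace the death sentence with two statements:

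1. For subjects who died on treatment, DI is replaced by the smaller of DI and (death date − last dose date).
2. Subjects who discontinued study drug before death follow the discontinuation rule.

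This keeps the apparent purpose, since deaths inside DI still truncate it. It also treats a death during a dose hold in the same way as a discontinuation at the same point. The cost is two sentences in the SAP and a minimum function in the derivation, with no new data to collect.

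### The SAP's stopping rule for duration of therapy differs between Schedule A and Schedules B and C, so fully compliant patients who stop early inside a dosing block get a relative dose intensity category that depends on their schedule

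*SAP*

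**What the plan says.** SAP 7.4.1.1 (Summary 2) defines duration of therapy in weeks as last dosing date minus first dosing date plus DI, divided by 7. Dose intensity is cumulative dose over that duration, and RDI "is the ratio of the dose intensity (mg/week) to the planned dose level per week". RDI is tabulated by treatment in five categories: below 50%, 50 to below 70%, 70 to below 90%, 90 to below 110%, and 110% or more.

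DI is 1 day during dosing days in all schedules. Near the end of a block it becomes the rest period:
- Schedule A: "after 4th consecutive dose for 7 day cycle, DI=2 days"
- Schedule B: "after 13th consecutive dose for 14 day cycle, DI=7 days"
- Schedule C: "after 6th consecutive dose for 7 day cycle, DI=14 days"

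Patients who discontinue or are lost to follow-up have their own rule. In Schedule A, DI is 1 after three or fewer of the five doses, "and DI= 2 if they received 4 or 5 doses". In Schedule B, "DI will still be set to 7 days if discontinued or lost to followup". In Schedule C, "using Schedule C, DI will still be set to 14 days if discontinued or lost to followup". Deaths are handled separately, "by using instead of DI the number of days between the death date and the last dose date". The single Part 1 Cycle 1 dose is left out of the exposure summary, and the clock starts at Cycle 2 Day 1.

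**The concern.** For patients who stop, Schedule A's DI depends on where in the block they stopped. In B and C it does not: a patient who stops in the middle of a block is credited with a rest period never reached. Either convention could be defended on its own, but mixing them puts a schedule-dependent number in the RDI denominator.

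Part 1 compares schedules, and RDI is where a reader looks to see how much of the planned drug each schedule delivered. A compliant early stopper can look over-dosed in A and under-dosed in B or C purely by convention. In A the rule can also hide a missed dose.

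**Working it through.** **Inputs.** The DI values are those of SAP 7.4.1.1. SAP 7.4 gives 5 doses per 7 days (A), 14 per 21 days (B) and 7 per 21 days (C). The SAP gives no number for planned dose per week, so I take the cycle average: 5, 14/3 and 7/3 doses per week. The Cycle 1 dose is excluded. The mg dose cancels at a constant level. The SAP states no RDI figure to reproduce.

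**Formula.** RDI = 100 × (doses × 7 / (last day − first day + DI)) / planned doses per week.

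**First block, no missed dose.** Five doses span 4 days:
- A: 5 × 7 / (4 + 2) / 5 = 116.7%
- B: 5 × 7 / (4 + 7) / (14/3) = 68.2%
- C: 5 × 7 / (4 + 14) / (7/3) = 83.3%

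| Doses taken, then stopped | A | B | C |
|---|---|---|---|
| 1 | 140.0% | 21.4% | 21.4% |
| 3 | 140.0% | 50.0% | 56.3% |
| 4 | 112.0% | 60.0% | 70.6% |
| 5 | 116.7% | 68.2% | 83.3% |

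At 4 and 5 doses all three categories differ. At 1 and 3 doses B and C share one and A differs.

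**How far it reaches.** Stopping points outside 90 to below 110%, with no missed dose:
- A: doses 1 to 5 and dose 8 (112.0%), all at 110% or more: 6 points.
- B: the first 8, 5 and 1 doses of blocks one to three, all below 90%: 14 points.
- C: the first 5, 4, 3, 2 and 1 doses of blocks one to five, all below 90%: 15 points.

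**Stops after a completed cycle.**
- A: 20 × 7 / (25 + 2) / 5 = 103.7%
- B: 14 × 7 / (13 + 7) / (14/3) = 105.0%
- C: 7 × 7 / (6 + 14) / (7/3) = 105.0%

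All fall in the right category. They exceed 100% because DI counts rest days (2, 7, 14), not days to the next dose (3, 8, 15); that is one day in every schedule.

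**Nominal first scan, B and C.** Week 9 is 63 − 7 = 56 days after Cycle 2 Day 1, which is day 15 of the third 21-day cycle. The patient has completed three blocks and is in a rest period. Both durations are 62 days (B 42 + 13 + 7; C 42 + 6 + 14), and both RDIs are 101.6%.

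**Missed dose hidden in A.** Four of five scheduled doses, the last on day 5, gives 4 × 7 / (4 + 2) / 5 = 93.3%. The true proportion is 80.0%, one category lower.

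**Sensitivity, five doses.** Counting the Cycle 1 dose in the numerator gives A 140.0%, B 81.8%, C 100.0%, still three categories; A's stopping points at 110% or more rise from 6 to 16. Reading planned dose as the on-week rate (7 per week in B and C) gives 116.7%, 45.5% and 27.8%: A still differs, but B and C share a category.

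**The case against.** The strongest reply is that few patients need be affected. Protocol 1.4.4 reports 81 treated patients, of whom 68 stopped for progression. Scans are scheduled at 8 weeks (A) or 9 weeks (B, C), each ±7 days. A compliant A or B patient who stops anywhere in that window is in 90 to below 110%; in C the only exception is the last window day (85.7%). This stands as a limit on size. Stops between scans for toxicity, clinical progression or withdrawal remain possible, and the documents do not say how many occurred inside a block.

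A second reply is that the B and C bullets might apply only to patients already past the block, leaving DI at 1 for stops within it. The word still reads more naturally as overriding that value. On the alternative reading, B and C would score 150% and 300% anywhere in the first block, so the table would still be wrong.

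Third, the SAP also provides dose counts, cumulative dose, modifications with reasons and individual listings. A reader could trace individuals through these, but the category table itself would remain incorrect.

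A reader might infer that every compliant patient is miscategorised, or that exposure cannot be compared across schedules at all. The documents do not support that: stops after whole cycles land in the correct category in all three schedules.

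**Conclusion.** The point holds for patients with no missed dose who stop early and inside a dosing block. Their RDI category depends on the schedule's stopping rule: five doses give 116.7%, 68.2% and 83.3%; one dose gives 140%, 21.4% and 21.4%. These figures rest on the cycle-average planned dose and on excluding the Cycle 1 dose. The counts of affected stopping points change if that dose is included, but a schedule difference remains under each reading tried.

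A reader might also infer that schedule or dose selection is compromised. It is not shown to be: no DLT, MTD, sample-size or efficacy result uses RDI, and the tables are descriptive. Nor does Part 2 show a between-schedule problem, because the Initial Expansion uses Schedule A only. The SAP merely leaves unstated how the two Part 2 dose levels enter the planned weekly dose. The change is worth making because a stated rule yields wrong categories and is cheap to correct.

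**What to change.** Define RDI as 100 × cumulative dose taken / cumulative dose scheduled, both over the same window. Start at Cycle 2 Day 1 in Part 1, with the Cycle 1 dose excluded from both terms, and at Cycle 1 Day 1 in Part 2. End at one stated point for all schedules: the last dosing date, or the decision to discontinue used in SAP 6.1.2. The first ignores doses held before a permanent stop; the second counts them. Either removes the schedule artefact. Setting DI to 1 everywhere would not: the first block would give 140%, 150% and 300%.

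Also state:
- that the Part 2 scheduled dose is the two-level sequence already in SAP 6.2;
- how patients who change schedule under Protocol 4.5.2, who stay classified by original arm, are counted;
- how delayed cycles are counted.

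Use one duration-of-therapy rule for all schedules and all reasons for stopping, including death, and do not use it as the RDI denominator. The general rule in SAP 8.1 (last date minus first date plus 1) is a candidate, though it counts a completed Schedule C cycle as 7 days. If mg/week is kept, report it as cumulative dose divided by that duration.

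The cost is SAP wording and a small programming change, with no new data.

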#### **Listing:**

- Drug administration of BMS-986158
- Duration of therapy (weeks) , cumulative dosing, dosing intensity, and relative dose intensity

#### **7.4.1.2 Modification of BMS-986158 Therapy**

#### **Summary:**

- Descriptive statistics will be provided by treatment and overall for:
  - Number (%) of subjects with dose modifications with reasons.

#### **7.4.2 Concomitant Medications**

Concomitant medications, defined as medications other than study medications which are taken at any time on-treatment (i.e. on or after the first day of study therapy and within 100 days following the last dose of study therapy), will be coded using the UMC WHO Drug Global Dictionary. Concomitant medication by-subject listing will be provided.

## 7.5 Efficacy

- PCWG3 criteria is intended for Part 2 subjects and not Part 1 subjects. Lugano and PCWG3 criteria will be used if relevant data is available.
- The primary efficacy analyses will be performed on All Treated Population for the final analysis. Efficacy analyses based on the Response-evaluable Population may be performed as supportive analyses. If the majority of All Treated Population is included in Response-evaluable Population, limited efficacy analyses will be performed on Response-evaluable Population (e.g., ORR).
- For interim analyses when the minimum follow-up period is less than sufficient to warrant adequate interpretation of the result, efficacy analyses may be performed on Response-evaluable Population.
- Efficacy results will be presented by treatment and overall, for each tumor type. For efficacy endpoints, treatment comprises dose schedule.
- Efficacy will be reported based on investigator BOR. Investigator reported CR or PR was not always confirmed by a second scan. Therefore, ORR summaries will be presented regardless of confirmation.

Time-to-event distributions (e.g. for progression free survival, [REDACTED] and duration of response) will be estimated using K-M methodology. When appropriate, the median along with 95% CI will be provided using Brookmeyer and Crowley methodology (i.e., using log-log transformations for the construction of confidence intervals).

Rates at fixed time points (e.g. PFSR at 24 weeks or OS at 12 months) will be derived from the K-M estimates and corresponding confidence intervals will be derived based on the Greenwood formula. Confidence intervals for binomial proportions will be derived using the Clopper-Pearson method. Additional time points will be considered based on data availability.

### **Summary:**

The following will be summarized by treatment and overall, for each tumor type.

- ORR with corresponding 2-sided 95% CI based on Clopper-Pearson method along with each category of BOR
- Duration of response (DOR) with median (95% CI using the log-log transformation method) and range (min, max) by K-M method. The number of subjects still in response at the time of database lock will be indicated. If the number of responders per tumor type is too small (e.g., 5 or less confirmed CR or PR in a tumor type), DOR will not be presented.
- PFS with median (95% CI) and range (min, max) by K-M method. The number of subjects still progression free at the time of database lock will be indicated.
- PFSR at specified timepoints (e.g., Week 24, Week 48) by K-M method using the Greenwood formula for confidence intervals

### **Figure:**

- Percent change from baseline in target lesions over time (aka spider plot)

- Best change in baseline target lesions (aka waterfall plot)
- K-M plot of duration of response for responders only (if sufficient number of responders, i.e. more than 5 confirmed CR or PR in a tumor type)
- Swimmer plot of time to response, duration of response and tumor progression for all participants
- K-M plot of PFS
- K-M plot of OS

**Listing:**

The following will be listed by treatment and tumor type as appropriate.

- Tumor lesion measurements
- Tumor evaluation at each visit
- Participant level efficacy for all treated participants- tumor best overall response (BOR), best change in tumor burden, PFS, death indicator
- Duration of response for responders - BOR, time to response, time on therapy, response duration

- Subsequent therapy

## **7.6 Safety**

Analyses of safety will be based on All Treated population and will be presented principally by treatment (“as treated”) and overall unless otherwise indicated. Deaths will be summarized by schedule.

Adverse events (AEs) will be coded according to the most current version of MedDRA and be graded using the NCI Common Terminology Criteria for Adverse Events (CTCAE) version 4.03. Drug-related AEs are those events with relationship to study drug “Related” as recorded on the CRF. If the relationship to study drug is missing, the AE will be considered to be drug-related.

Listing of AEs will include all enrolled subjects as well as SAEs and deaths, which are collected pretreatment. Summaries of AEs will include (1) events occurring from the first dose date to 30 days (inclusive) after the last dose of BMS-986158 monotherapy for subjects who are off study treatment and (2) all events occurring from first dose date for subjects who are still on study medication. AEs and treatment-related AEs will be tabulated by descending frequency of SOC and descending frequency of PT within each SOC, unless specified otherwise.

When reporting adverse events by CTC grade, summary tables will be provided based on events’ worst CTC grade (independently of relationship to study medication). Subjects will only be counted (1) once at the preferred term (PT) level, (2) once at the system organ class (SOC) level, and (3) once in the ‘Total subject’ row at their worst CTC grade, regardless of SOC or PT.

Unless otherwise specified, the AE summary tables will be restricted to on-treatment events regardless of the causality.

The analysis of laboratory results will be based on the All Treated population in participants with data. Laboratory results will be categorized according to NCI CTCAE (version 4.03) grade. Baseline is defined as the last non-missing measurement prior to the first dosing date and time. Summaries of laboratory results include baseline and (1) post-baseline results up to 30 days (inclusive) after the last dose of BMS-986158 monotherapy for subjects who are off study treatment and (2) all available post-baseline results for subjects who are still on study medication. Vital signs and clinical laboratory test results will be listed and summarized by treatment. Any significant physical examination findings and clinical laboratory results will be listed. ECG readings will be evaluated by the investigator and abnormalities, if present, will be listed.

